2.2 Rationale

Therefore, the next logical step in the evaluation of AQ-13 is to determine whether it is active against CQ-resistant *P. falciparum* infection in human subjects. The hypotheses underlying this protocol are that: 1] an AQ-13 dose of 1596 mg administered orally will be efficacious for the treatment of uncomplicated *P. falciparum* malaria in human subjects, and 2] the bioavailability, pharmacokinetics and adverse events (AEs) of AQ-13 in human subjects with uncomplicated malaria will be similar to those observed previously in healthy uninfected subjects during the Phase 1 studies [11].

The rationales for the selection of adult men for this Proof of Efficacy Study with AQ-13 are that: 1] the involvement of only males will obviate potential concerns about inadvertent pregnancies in female volunteers who have agreed to contraception and 2] that persons who have survived to adulthood in Mali are protected against life-threatening complications and death from malaria because they have acquired the semi-immune state [12]. Therefore, if for reasons we have not foreseen, AQ-13 does not work (if AQ-13 is not effective for treatment of uncomplicated malaria in human subjects), the risk of severe disease or death in these subjects will still be extremely low – because they are protected by their previous acquisition of the semi-immune state.

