8.5.4 Type and Duration of the Follow-up of Subjects after Adverse Events

Mild AEs known to occur with both AQ-13 and malaria (e.g., headache, nausea, vomiting, myalgias, arthralgias) and other AEs will be followed daily until they have resolved and treated symptomatically as described in Table 2 on page 23 (acetaminophen for headache and for muscle and joint pains; antiemetics for nausea or vomiting).

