10 STATISTICAL CONSIDERATIONS

10.1 Study Outcome Measures

The primary, secondary and tertiary objectives (Section 3, above) and outcome measures (Section 8, above) in this study will be assessed statistically as outlined below (Table 7).

Table 7.

Statistical Assessment of Study Endpoints

COMPONENTS OF THE PRIMARY ENDPOINT

- Lack of recrudescence at 42 days
- < 25% of baseline asexual parasitemia on day 3
- Clearance of asexual parasitemia and fever by day 7

STATISTICAL TESTS

- Pearson χ^2 , Fisher Exact test
- Pearson χ^2 , Fisher Exact test
- Pearson χ^2 , Fisher Exact test

SECONDARY ENDPOINTS

- Adverse Events (AEs) Pearson χ^2 , Fisher Exact test
- Effects on the QT (QTc) Interval (within individuals) Wilcoxon, Friedman test
- Effects on the QT (QTc) Interval (between groups) ANOVA, Kruskal-Wallis test
- Pharmacokinetic Parameters for Parent Compounds (AUC_t, t_{1/2}, Vd/F, Cl/F, MRT) Mann-Whitney, Kruskal-Wallis
- Time to parasite Clearance, Recrudescence or Reinfection (between groups) Kaplan-Meier, Cox Hazard
- Time to fever clearance (between groups) Kaplan-Meier, Cox Hazard

TERTIARY ENDPOINTS

- Pharmacokinetics of metabolites as above
- Aminoquinoline (chloroquine) pruritus Fisher Exact test

AUC_t = total area under the curve; t_{1/2} = elimination half-life; Cl/F = oral clearance; Vd/F = oral apparent volume of distribution; MRT = mean residence time.

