Times to recrudescence and reinfection will be analyzed using life tables, and compared using the log rank test. Cox regression will be used to compare multiple (multivariate) predictors of times to recrudescence and reinfection. Pharmacokinetic parameters will be examined for AQ-13 doses and compared to data from the Phase 1 studies, as appropriate. **Using the same protocol as in the Phase 1 study [11], the relatedness of adverse events (AEs) to study drugs will be classified independently by two blinded physicians according to the definitions in section 8.3 on page 30 as unknown, not related, unlikely to be related, or possibly, probably or definitely related to the study drugs, based on temporal relationships and biological plausibility.** The frequencies of AEs will be compared between AQ-13 and Coartem using Pearson Chi-square. Because more than one AE may occur in an individual patient, the proportion of patients receiving AQ-13 with AEs will be compared with Coartem using Chi-square or the Fisher Exact test. The severity of AEs will be classified using the recent FDA Guidance for Healthy Adult and Adolescent Volunteers in Preventive Vaccine Trials [23], and the severity of AEs across the study arms will be compared using Chi-square. QT interval corrections for heart rate (QTc) will be made using both Bazett's and Fridericia's formulas [41-42]. Within-patient maximum changes from baseline will be assessed using the Wilcoxon test for paired observations. Between-group QT interval changes will be compared using ANOVA or Kruskal-Wallis.

HYPOTHESES BEING TESTED.

The primary hypothesis is that the efficacy of AQ-13 for uncomplicated *P. falciparum* malaria is similar to

that of Coartem - based on a non-inferiority margin of 15%. That is, that AQ-13 will produce a cure rate within 15% of the Coartem control (standard). The secondary hypothesis is that AQ-13 will have safety profiles in subjects with uncomplicated malaria comparable to those for AQ-13 in healthy volunteers [11].

EXPECTED OUTCOMES.

Our preliminary (previous) studies have shown that AQ-13 is:

- *active in vitro* against CQ-resistant and multi-resistant *P. falciparum* [8-9],
- *active in vivo* against CQ-resistant *P. falciparum* in the squirrel monkey model of human infection with CQ-resistant *P. falciparum* (enclosed Figures 1 and 2 in the Appendix), and
- *safe in human subjects* based on Phase 1 studies recently performed in New Orleans [11].

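### The stated secondary safety hypothesis (AQ-13 in malaria comparable to AQ-13 in healthy volunteers) has no planned test, and the difference tests listed for AEs and PK cannot support a finding of similarity

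*Combined protocol and SAP*

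**What the plan says.** - **Underlying hypothesis (Sections 2.2 and 3).** The second of two hypotheses is that bioavailability, PK and AEs of AQ-13 in malaria "will be similar to those observed previously in healthy uninfected subjects during the Phase 1 studies".
- **Hypotheses listed as being tested (Section 10.3).** "The secondary hypothesis is that AQ-13 will have safety profiles in subjects with uncomplicated malaria comparable to those for AQ-13 in healthy volunteers". PK is not mentioned there.
- **AE analyses (Section 10.3).** AE frequency and the proportion of patients with AEs are compared between AQ-13 and Coartem by chi-square or Fisher's exact test. AE severity is compared across the study arms by chi-square. No AE analysis against Phase 1 is described.
- **Expected outcomes (end of Section 10.3).** Safe is explained as AQ-13 having AEs similar to those of Coartem in this study.
- **PK analyses.** Section 10.3: "Pharmacokinetic parameters will be examined for AQ-13 doses and compared to data from the Phase 1 studies, as appropriate". Table 7 in Section 10.1 has a row for "Pharmacokinetic Parameters for Parent Compounds" with the tests "Mann-Whitney, Kruskal-Wallis".
- **Assays and doses.** Section 6.2.2 lists an HPLC assay for AQ-13 and its metabolites only. Section 10.3 describes one AQ-13 dose.
- **Overlap of drug and disease.** Section 8.5.4 refers to "Mild AEs known to occur with both AQ-13 and malaria", giving headache, nausea, vomiting, myalgias and arthralgias as examples.
- **Margins.** The only margin in the plan is 15 percentage points on the cure rate.

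**The concern.** There are two separate faults.

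**The hypothesis and the tests have different comparators.** The secondary hypothesis compares AQ-13 in patients with AQ-13 in healthy volunteers. The tests compare AQ-13 with Coartem. Whatever those tests show, the hypothesis as written stays untested, and a report could move between the two comparators without the plan ruling it out.

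**The tests answer a different question.** The plan wants to say similar or comparable, but chi-square, Fisher, Mann-Whitney and Kruskal-Wallis test for a difference. In a trial of this size a non-significant result is likely even when a material difference exists. For cure rate the plan handles this properly, with a margin and a confidence interval. For AEs and PK it gives no limit, no interval and no decision rule.

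At stake is what may be concluded about safety and exposure in the first study of AQ-13 in patients. The primary efficacy conclusion does not depend on it.

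**Working it through.** **1. The plan's own figure.** No sample size, power or limit is stated for this hypothesis, so there is nothing to reproduce. The stated 33 per group comes from the cure-rate calculation (26 evaluable; 26/0.8 = 32.5, rounded up to 33).

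**2. Comparators side by side.**

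| Item | Section | Comparator |
|---|---|---|
| Secondary hypothesis, safety | 10.3, hypotheses | Healthy Phase 1 volunteers |
| AE frequency, patients with AEs, severity | 10.3 | Coartem |
| Expected safety outcome | 10.3, end | Coartem |
| PK parameters | 10.3 | Phase 1, no test named |
| PK parameters | Table 7 | Not named; rank tests |

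No row joins the safety hypothesis to a test.

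**3. What the AE test can miss.** Inputs: 33 per arm (Section 10.2); two-sided 5% level and AE risks assumed, because the documents give neither. The probability of a non-significant result is the sum, over all pairs (i, j), of Bin(i; 33, p1) × Bin(j; 33, p2) for pairs with p > 0.05.

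| Coartem risk → AQ-13 risk | Missed, Fisher | Missed, Pearson chi-square |
|---|---|---|
| 10% → 20% | 88% | 79% |
| 15% → 30% | 79% | 68% |
| 20% → 40% | 68% | 56% |
| 25% → 50% | 52% | 41% |

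**4. What an interval would show.** The 95% half-width for a risk difference is 1.96 × √[p1(1−p1)/33 + p2(1−p2)/33].
- Both risks 15%: 1.96 × √(0.1275/33 + 0.1275/33) = 17 points.
- Risks 30% and 15%: 1.96 × √(0.21/33 + 0.1275/33) = 20 points.

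The interval makes visible how much is left open; a p-value above 0.05 does not.

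**5. PK against Phase 1.** Inputs: 26 evaluable AQ-13 patients (Section 10.2; Section 5.1 says 28). The PK coefficient of variation (CV) and the number of Phase 1 subjects at a comparable AQ-13 dose are not given, so I assume CV 30–60% and 15 to 30 subjects. On the log scale s = √ln(1+CV²). The probability of missing a 25% lower AUC comes from simulated two-sided 5% Mann-Whitney tests. The last column is the chance that the 90% CI lies inside assumed limits of 0.80–1.25 when the true ratio is 1.

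| CV | 25% lower AUC missed (26 vs 30 to 26 vs 15) | 90% CI inside 0.80–1.25 (26 vs 15 to 26 vs 30) |
|---|---|---|
| 30% | 6–19% | 49–75% |
| 40% | 24–41% | 11–38% |
| 60% | 54–67% | 0–1% |

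The 90% CI factor is exp(t × s × √(1/n1 + 1/n2)). At CV 40%, s = √ln(1.16) = 0.385:
- 26 vs 15: exp(1.685 × 0.385 × 0.324) = 1.23, so an observed ratio of 1 has the interval 0.81–1.23.
- 26 vs 30: exp(1.674 × 0.385 × 0.268) = 1.19, so 0.84–1.19.

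**6. Dose normalisation.** Cl/F is dose/AUC, so it already contains the dose, and dose-normalised AUC is its reciprocal; only one of the two is needed. Sections 10.2 and 10.3 give a total of 1596 mg. Flow Chart 3 gives 700 + 700 + 350 = 1750 mg, and Flow Chart 4 also states 1750 mg. Since 1750/1596 = 1.096, the choice of total moves a dose-normalised ratio by about 10%.

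**The case against.** The strongest replies are these.

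- **A reader might infer that the plan will declare PK similarity from a non-significant rank test.** The documents do not say so. The Phase 1 sentence in Section 10.3 names no test, and Table 7 does not assign its rank tests to the Phase 1 comparison. What stands is that Table 7 offers nothing else for PK, and that only AQ-13 and its metabolites are assayed, at one dose.
- **A reader might infer that PK similarity is a formally tested hypothesis.** It is an underlying hypothesis in Sections 2.2 and 3; the list in Section 10.3 covers efficacy and safety only. The PK objective itself is to measure parameters.
- **A reader might infer that no rank test on PK is possible within the trial.** That goes too far. Contrasts inside the AQ-13 arm, such as by chloroquine susceptibility, could be made, although the plan does not assign the tests to them.
- **Coartem is the better AE comparator.** I agree. It is concurrent and randomised, and malaria symptoms overlap with the common AEs. This is why the hypothesis should change rather than the tests. Using the Phase 1 criteria for relatedness, applied by blinded physicians, helps a descriptive comparison but does not separate drug from disease.
- **The PK figures rest on assumptions.** They do. At CV 30% a 25% deficit is missed in only 6–19% of studies.

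None of this supplies a test of the safety hypothesis as written, or makes a difference test evidence of similarity.

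**Conclusion.** The point holds in this form: the safety hypothesis in Section 10.3 has no matching analysis, and the tests listed for AEs and PK cannot by themselves support similar or comparable. The mismatch is read directly from the text and needs no assumption.

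The size does rest on assumptions. At 33 per arm, a rise from 15% to 30% in patients with AEs would be missed in about 79% of trials (Fisher) or 68% (chi-square); across assumed control risks of 10–25%, a doubling is missed in 41–88%. For PK, a 25% lower AUC is missed in 6–67% of studies, depending on the assumed CV and Phase 1 group size.

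It would be too strong to say that the plan can say nothing about Phase 1. A descriptive side-by-side comparison remains possible; what is missing is a basis for a formal similarity conclusion. This is worth correcting before analysis, but it does not touch the primary endpoint.

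**What to change.** 1. **Safety hypothesis.** Restate it in Section 10.3 as AQ-13 versus concurrent Coartem, in line with the expected outcomes. Report the risk difference in patients with AEs with a 95% CI, and state that similarity will not be concluded from a non-significant test.
2. **Phase 1 AE comparison.** Make it descriptive, and cite the overlap with malaria symptoms noted in Section 8.5.4.
3. **PK.** In Table 7, replace the rank tests with geometric mean ratios (malaria / Phase 1) and 90% CIs for dose-normalised AUC and Cmax. Cl/F, without dose-normalisation, may be used in place of AUC. Name the Phase 1 dose group and its size. Label the comparison non-randomised and descriptive, and claim similarity only if limits are set in advance.
4. **Dose.** Reconcile the stated AQ-13 totals (1596 mg in Sections 10.2 and 10.3; 1750 mg in Flow Charts 3 and 4) before any dose-normalised comparison.

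**Cost.** Items 1 to 3 are changes of analysis wording and use Phase 1 data that the plan already intends to compare with; item 4 is a reconciliation of the protocol text. The drawback is that similarity becomes harder to claim. With assumed limits of 0.80–1.25 and truly equal exposure, the PK interval would fall inside them in only 11–38% of studies at CV 40%, so a descriptive label is the realistic default.

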7.1.2 Secondary Outcome Measures

- 1] Adverse Events (AEs) – within 4 weeks of treatment as judged by **blinded** physician reviewers to be possibly related to the study drug(s) using the same criteria as in the Phase 1 study.
- 2] Parasite clearance time – from the initiation of treatment to the first of 2 successive negative smears.
- 3] Time to recrudescence or reinfection – time from the initiation of treatment to the reappearance of asexual *P. falciparum* parasites on the thick smear.
- 4] Effects on the QT (QTc) interval – mean changes from the baseline pre-treatment QT (QTc) interval to the post-treatment QT (QTc) interval after treatment with AQ-13 or Coartem.
- 5] Pharmacokinetic parameters for AQ-13 – these will include measurements of AQ-13 blood levels over time (peak levels, AUC, MRT), drug distribution (Vd/F) and drug elimination ($t\frac{1}{2}$, Cl/F).
- 6] Fever clearance time: Time in hours from the initiation of therapy until disappearance of fever for at least 24 hours.

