8.4 Assessment of Adverse Events

8.4.1 Detection of Adverse Events

Detection of adverse events (AEs) will be based on twice daily interviews during the inpatient stay and on interviews during each of the outpatient visits. At these times, the physician will ask about common symptoms such as headache, dizziness, nausea and any other symptoms or signs patients may have. Please note that patient diaries (which were used during the Phase 1 studies in New Orleans) are unlikely to be useful (although they will be offered) because we expect that > 90% of the study participants will be illiterate.

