10.2 Sample Size Considerations

The proposed sample sizes are 33 per group for a total of 66 subjects in 2 treatment groups (one AQ-13 group receiving 1596 mg orally + one Coartem control group) for this Proof of Concept Study of AQ-13 in adult Malian males \geq 18 years of age with uncomplicated malaria (Flow Charts 2-3 on pages 16-17 and Flow Chart 4 on page 26).

Because sample sizes vary markedly with the efficacy of the comparator, accurate estimation of the Coartem cure rate is a key issue. The sample sizes estimated were based on an expected efficacy (cure rate) of 95% for Coartem [20-22, 25-27] and a conservative 20% estimate of attrition after treatment. An expected cure rate of 95% has been used for Coartem because this estimate is at the lower end of the range of cure rates reported in the recent literature (93.9%, 95.5%, 97.1%, and 97.5%) [20-22, 36], and because it simultaneously recognizes recent concerns about *in vivo* selection by Coartem for the 86N allele of *pfmdr1* in *P. falciparum*, which has the potential to further reduce the cure rate [37-38].

Another major factor is the width of the non-inferiority margin (M), the range within which the investigational drug is considered non-inferior to the comparator (control). We have used a value of $M = 15\%$. In the recent Guidance Document “Non Inferiority Clinical Trials” [Mar 2010], M equal to 40% of the efficacy of the positive control is stated to be a statistically persuasive result for phase III trials of drugs in general and elsewhere in this document it is stated that a non-inferiority margin of 50% for cardiovascular drugs is equivalent to a non-inferiority margin of 10-15% for antibiotics. From these statements, we infer that for a candidate antimalarial such as AQ-13, a non-inferiority margin of 10-15% would be statistically persuasive for a phase 3 trial, in which case this margin should also be sufficient for the present Phase 2 Proof of Concept Efficacy Trial of AQ-13.

With $M=15\%$, a Coartem efficacy assumed to be 95% and a dropout rate up to 20%, a table from Machin and Campbell [Statistical tables for the design of clinical trials. Blackwell, Oxford: 1987, pp. 35-53] gives 33 patients per group as a sample size [80% power] (an excerpt from that table is provided as Table 8).

Table 8.
Effects of the Margin and the Dropout Rate on Sample Sizes
necessary to test for Non-Inferiority of AQ-13 to Coartem

Non-Inferiority Margin	Dropout Rate (percent)		
	0%	10%	20%

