10.3 Analysis Plan

This is a Proof of Concept Efficacy Study of AQ-13 in comparison to the gold standard (Coartem). Thus, this study in adult Malian males can be viewed as a non-inferiority study, comparing one dose of AQ-13 (1596 mg orally over 3 days) to Coartem [39].

The null and alternative hypotheses to be tested are:

$$H_0 = (C - E) \geq M \quad (\text{control is superior to experimental})$$

$$H_1 = (C - E) < M \quad (\text{experimental is not inferior to control})$$

C is the efficacy of the comparator (Coartem), E the efficacy of the investigational drug (AQ-13) and M the non-inferiority margin. $M = 15\%$ will be used (see above). AQ-13 will be considered equivalent to (not inferior to) the comparator (Coartem) if the null hypothesis is rejected with a one-sided alpha of 0.025 [29, 40]. Cure rates, adjusted for reinfection, will be calculated for AQ-13 and Coartem and differences between cure rates with AQ-13 and Coartem will be calculated with 95% confidence intervals. Non-inferiority of AQ-13 will be established if the upper limit of the 95% CI for the difference between AQ-13 and Coartem is less than the non-inferiority margin of 15% [28-29].

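### Section 10.3 does not name the patient as the unit for its chi-square tests of AE frequency and severity; if AEs are counted, within-patient clustering can inflate the type I error

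*Combined protocol and SAP*

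**What the plan says.** Section 10.3 plans three AE comparisons between the arms.

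1. Frequency: "The frequencies of AEs will be compared between AQ-13 and Coartem using Pearson Chi-square". No unit is given.
2. Patients affected: "Because more than one AE may occur in an individual patient, the proportion of patients receiving AQ-13 with AEs will be compared with Coartem", by chi-square or the Fisher exact test.
3. Severity, graded on an FDA toxicity scale: "the severity of AEs across the study arms will be compared using Chi-square". No unit is given, and there is no rule for reducing several AEs in one patient to a single grade.

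The endpoint table in section 10.1 (Table 7) does not settle the unit. Its entry begins "Adverse Events (AEs) Pearson" and then adds Fisher's test. The plan does not say whether comparison 1 or 2 takes precedence, and it sets no significance level for AE tests.

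AEs are the first-listed secondary outcome in section 7.1.2. They are counted "within 4 weeks of treatment as judged by" blinded physicians to be possibly drug-related. Section 8.4.1 bases detection on repeated questioning: "based on twice daily interviews during the inpatient stay and on interviews during each of the outpatient visits".

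**The concern.** Pearson's chi-square needs independent units. The reason given for comparison 2 is that one patient can have several AEs. That implies comparison 1 is not already per patient, since otherwise comparison 2 would be redundant. In comparison 3 the graded object is the AE itself, and section 8.4.2 likewise has the assessors grade the AEs observed.

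Some clustering is likely. Section 2.3.1 expects headache, dizziness and several digestive symptoms, and section 8.5.4 notes that some of the mild AEs also occur with malaria. Such symptoms plausibly occur together in the sicker patients, and twice-daily interviews give many chances to record them.

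With 33 patients per arm, a few patients who report many symptoms could then produce an apparent difference between the arms in the first secondary endpoint. For severity, the plan offers no patient-level result against which to check it.

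**Working it through.** **Inputs from the documents.** Section 10.2: "The proposed sample sizes are 33 per group for a total of 66 subjects in 2 treatment groups". The only significance level in section 10.3 belongs to the primary test: "if the null hypothesis is rejected with a one-sided alpha of 0.025". The documents state no AE rate, number of AEs per patient, within-patient correlation or error rate for the AE tests, so there is no figure of the plan's own to reproduce.

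**Assumptions.** Two-sided 5% for the AE tests; no true difference between arms; AEs per patient with mean 1–5 (counts) or 2–5 (severity); the degree of clustering varied from none upward.

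**Event counts.** Let T1 and T2 be the AE totals in two arms of n patients, with mean μ AEs per patient and variance-to-mean ratio VMR. Tested against an equal split, the statistic is (T1 − T2)² / (T1 + T2). Under no difference, the numerator has expectation 2nμ·VMR and the denominator 2nμ. The statistic therefore behaves like VMR times a chi-square on 1 degree of freedom, and

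type I error ≈ 2 × [1 − Φ(1.96 / √VMR)].

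For negative-binomial counts with shape k, VMR = 1 + μ/k. With μ = 3, k = 2 gives 2.5 and k = 1 gives 4. Simulation used 10,000 trials per setting:

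| VMR | 1.96/√VMR | Formula | Simulated |
|---|---|---|---|
| 1 (Poisson) | 1.96 | 0.050 | 0.047–0.051 |
| 1.5 | 1.60 | 0.110 | 0.111 |
| 2 | 1.39 | 0.166 | 0.159–0.167 |
| 2.5 | 1.24 | 0.215 | 0.219 |
| 3 | 1.13 | 0.258 | 0.256–0.260 |
| 4 | 0.98 | 0.327 | 0.329 |

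**Event-level severity.** Each AE received a latent normal score in which a share ρ of the variance belongs to the patient. Scores were cut into three grades at an assumed 60/30/10% split. Counts per patient were Poisson or negative-binomial (k = 1) with mean 2, 3 or 5, and there were 3,000 trials per setting:

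| ρ | Chi-square on AEs, range over settings |
|---|---|
| 0 | 0.038–0.054 |
| 0.1 | 0.054–0.109 |
| 0.3 | 0.091–0.242 |
| 0.5 | 0.124–0.357 |
| 0.8 | 0.214–0.554 |

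**Patient-level tests on the same simulated trials.**

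- Any AE, Pearson chi-square: 0.049–0.068 in most settings. It fell to 0.030 and 0.000 for Poisson counts with mean 3 and 5, where almost every patient has an AE (expected share without one: e⁻³ = 5% and e⁻⁵ = 0.7%).
- AE count per patient, Welch test: 0.044–0.052.
- Worst grade per patient, chi-square: 0.037–0.059.

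Moving to the patient therefore removes the inflation. The any-AE comparison alone says little if nearly everyone has an AE, which is a reason to pair it with worst grade. The rank-sum and exact trend tests were not simulated; the worst-grade result is for chi-square.

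**The case against.** **The unit is inferred.** The plan never says that events are counted. Comparison 2 could be read as explaining how comparison 1 will be done. Table 7 gives AEs the same pair of tests as the components of the primary endpoint, which are patient-level outcomes. A two-arm Pearson test also normally needs a with/without table, and the plan does not describe a test of bare totals against an equal split. This stands as a reason for caution. It does not remove the point: an analyst could follow either reading, and the severity sentence has no patient-level alternative.

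**The size is not in the documents.** This stands. The secondary endpoint covers only AEs judged possibly related within four weeks, so the number per patient could be low. A reader might infer that the false-positive rate is known to be several times nominal. The documents do not support that: without overdispersion or within-patient correlation there is no inflation.

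**A sound AE comparison is already planned.** This also stands. A reader might infer that the safety comparison rests on event counts alone, but section 10.3 does include the proportion of patients with AEs. What is missing is its precedence, and an equivalent for severity.

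**Little depends on these p-values.** Halting in section 8.6 (Table 4) uses numbers of AEs by grade and relatedness, and that section itself expects significance-based rules to be of little use. The secondary hypothesis compares AQ-13 with healthy volunteers. Where section 10.3 expects AEs similar to Coartem, an anti-conservative test works against that expectation. This stands in large part. The harm is a spurious contrast between the arms, in either direction, rather than false reassurance that they are alike.

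**Conclusion.** The point holds in a limited form. Section 10.3 leaves the unit undefined for AE frequency and severity, and its wording most naturally counts AEs. On that reading both chi-square tests ignore clustering within patients. The possible type I error runs from the nominal 5% to 22–33% for counts at VMR 2.5–4, and from about 4–5% to 9–24% for severity at ρ = 0.3. These ranges rest on assumed AE means, an assumed grade split and an assumed two-sided 5% level. The documents cannot say where in the ranges this trial lies.

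Severity is the stronger half, because the plan contains no patient-level version of it. The issue is confined to secondary safety comparisons; neither the primary non-inferiority conclusion nor the halting rules depend on it. The correction is worth making before the data are analysed.

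**What to change.** Amend section 10.3 and Table 7 as follows:

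- State that the patient is the unit of analysis for all between-arm AE tests.
- Name the proportion of patients with at least one AE, by Fisher's exact test, as the main AE comparison.
- Replace the AE-level severity chi-square with a comparison of each patient's worst grade between arms, by a Wilcoxon rank-sum or exact trend test. State how patients with no AE are ranked, for example as the lowest category.
- Report event counts descriptively. If a test of counts is wanted, use one that allows for clustering, such as a comparison of AE counts per patient.

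The cost is a wording change. The AEs are already recorded and graded by study number, so no new data or visits are needed and the sample size does not change.
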